9.0 Data and Specimen Long Term Storage and Use

9.1 *If you will store data or specimens for future use, describe where you will store the data or specimens, how long they will be stored, and how and by whom the data or specimens will be accessed:*

All participant data, including electronic data, will be stored in secure places to protect confidential participant information. Secured places will include locked filing cabinets, locked rooms accessible only to study personnel, and/or password-protected databases. Moreover, all data will be quality controlled in preparation for data analyses. All discrepancies in data entry will be checked against the raw data source, and the correct data entry will be used. All data entered into spreadsheets and databases will be coded by participant ID number and not by name (i.e., first and last name), stored in a master ID log. The master ID log will be stored in REDCap and Qualtrics, which are HIPAA compliant. Additionally, all entered data will be backed up on secure password-protected servers. Computers used in the studies will also be password protected, and accessible only by study personnel. Computers and password-protected servers used for this study are Virginia Tech secured and managed. We will provide certification of IRB approvals of the study protocol to NIDA prior to enrolling study participants. VT IRB regulations will be strictly adhered to in the conduct of the proposed research. Specifically, prior to implementation of any protocol changes, amendments will be submitted to the IRB for approval. Data will be stored for three years following publication in accordance with NIH policy. Individuals on the IRB approved protocol will have access to data in long term storage.

9.2 *For specimens, list the data to be stored or associated with each specimen:*

NA

9.3 Describe the procedures to release data or specimens outside of the research team, including the process to request a release, approvals required for release, who can obtain data or specimens, and what data will be provided with specimens:

Investigators will adhere to all NIH requirements regarding data sharing. Participant data collected in this project will be de-identified and made available if requested. We will also share the analysis results. As part of this process, all investigators will be required to agree to the following conditions: 1) will adhere to the reporting responsibilities; 2) will not redistribute the data beyond the requesting individual and named collaborators; 3) will give appropriate acknowledgement; 4) will not use the data for commercial purposes; and 5) will obtain appropriate ethical approvals.

Results from research conducted will be shared and disseminated, including: regular project meetings, annual meetings, symposia, workshops, and/or conferences for related groups. Manuscripts will be written and submitted for publication in peer-reviewed journals/conferences, following the NIH Public Access Policy guidelines. All necessary ethical approvals will be obtained.

Raw data will be made available upon request after the dissemination of results.

Access Criteria:

Data requests will be reviewed by the principal investigators and data will be shared with the expectation of acknowledgment of funding source and primary study team.

9.4 Describe the identifiers to be included with stored data or specimens, as well as any key or code that could be used to make them identifiable. Describe where the code will be stored, who will have access to it, and when it will be destroyed:

All screened participants are assigned study IDs that are thereafter associated with all collected data. The electronic de-identified data is stored on the [name] shared server which is password protected and only accessible to members of the research team on the VT IRB approved protocol.

Study ID and identifiers (i.e., name, email, age, and demographics) will be available together electronically only in the pre-screener in Qualtrics. Specifically, we will use a pre-screener survey in Qualtrics to collect demographic and other screening criteria to decide the participant's eligibility to enroll in the study. After completing the pre-screener, the participant will be assigned an ID. If eligible to enroll in the study, they will receive that ID by email together with the link to the surveys. They will use this ID to

authenticate their access to the two surveys of the study. They will not have to provide any PII during the surveys following the pre-screen. Throughout the remaining of the study, the only personal information linked to their ID will be their email which will be needed to send the survey links and process the payments. Data will be stored in Qualtrics and only authorized people will have access to the data in Qualtrics. If data need to be downloaded from Qualtrics, those data will be stored in password-protected folders and only the participant's ID will be included in the file. No other PII will be stored together with the participants' responses to the surveys.

9.5 Please select the identifiers you will obtain (whether directly from participants or from another source), including but not limited to:

	Name
	Geographical subdivisions smaller than a state, including street address, city, county, precinct, zip code, and equivalent geocodes (note, the initial three digits of a zip code are not considered identifiable)
	Elements of dates (except year) for dates directly related to an individual, including birth date, admission date, discharge date, date of death, and single year of age over 89 and all elements of dates (including year) indicative of such age (note, such ages and elements may be aggregated into a single category of age 90+)
	Phone numbers
	Fax numbers
	Electronic mail addresses (e-mail)
	Social Security numbers
	Medical record numbers
	Health plan beneficiary numbers
	Account numbers
	Certificate/license numbers
	Vehicle identifiers and serial numbers, including license plate numbers
	Device identifiers and serial numbers
	Web Universal Resource Locators (URLs)
	Internet protocol (IP) address numbers
	Biometric identifiers, including finger and voice prints (audio recording)
	Full face photographic images and any comparable images (including video recording)
	Student record number or identification number
	User name for online or computer accounts

	Any other unique identifying number, characteristic, or code (note this does not mean the unique code assigned by the investigator to code the data): Click here to explain.
--------------------------	---

10.0 Sharing of Results with Subjects

10.1 Describe whether you will share results (study results or individual subject results, such as results of investigational diagnostic tests, genetic tests, or incidental findings) with subjects or others (e.g., the subject's primary care physician). If so, describe how you will share the results and include this information as part of the consent document. Upload materials you will use to explain the results to subjects:

We will not share any results with the study participants. In the event of incidental findings, we will follow the established protocol highlighted in the NIDA Data and Safety Monitoring Plan (DSMP) for the R01 associated with this project.

11.0 Study Timelines

11.1 Describe:

- *The duration of an individual subject's participation in the study (for example, 1 hour, 2-4 weeks, 3-5 years).*
- *The amount of time expected to enroll all study subjects (weeks, months, years, etc.)*
- *The amount of time expected for the investigators to complete this study including primary data analyses.*

The study will last two online sessions of approximately 1h each.

12.0 Inclusion and Exclusion Criteria

12.1 Describe how you will screen individuals for eligibility. When will screening occur and what procedures will you use? Upload any screening scripts or surveys to Protocol Management:

We will use a study-specific pre-screening online survey that will occur prior to enrolling participants into the study, in order to effectively decrease attrition in our studies by ensuring that participants meet all inclusion/exclusion criteria prior to enrolling into the randomized study.

12.2 Describe the eligibility criteria that define who will be included and who will be excluded from enrollment for each procedure of your study.

Include any geographic criteria (e.g., Virginia Tech undergraduate students, a national sample of adults with engineering degrees, minors aged 8-12 in the New River Valley, university faculty in Virginia and Paris, France):

Inclusion criteria will require that participants:

(1) demonstrate high-risk or harmful drinking (AUDIT>15; i.e., 16 or higher); (2) be 21 years old or older, (3) have a desire to quit or cut down on their drinking, but do not have proximate plans to enroll in treatment for AUD during the study period

Exclusion criteria include: (1) having a current unmanaged psychotic disorder, (2) reporting current pregnancy or lactation, (3) having dementia

12.3 Indicate specifically whether you will include or exclude each of the following special populations: (You may not include members of these populations as subjects in your research unless you indicate them in the description of your subject population.)

- *Minors, as defined by state law where the study is performed (infants, children, teenagers)*
- *Pregnant women (can be included in minimal risk studies by mentioning in section 13.1)*
- *Prisoners (including all incarcerated individuals)*
- *Adults not capable to consent on their own behalf*

Vulnerable subjects, such as individuals with cognitive impairments, minors, prisoners, and pregnant women will be excluded.

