1.0 Study Summary

Study Title	Scarcity narratives and AUD
Study Design	Adults with Alcohol Use Disorder (AUD) will be enrolled in the study and complete two online sessions where the effects of exposure to scarcity narratives on delay discounting and alcohol demand will be investigated. Participants will be randomly assigned to one of two scarcity narrative groups (active or control), balanced by discounting rate and sex. Delay discounting and alcohol demand will be evaluated pre and post exposure to the narratives.
Primary Objective	The primary objective is to test the theory of Reinforcer Pathology via manipulation of the temporal window with exposure to a scarcity narrative. The primary outcome measures of this study are the extent to which scarcity narratives decrease an individual's temporal window and increase their alcohol valuation, compared to baseline.
Secondary Objective(s)	Investigate the effects of scarcity narratives on delay discounting and demand in individuals with AUD
Study Population	Individuals with Alcohol Use Disorder (AUD)
Sample Size	112
Research Intervention(s)/ Investigational Agent(s)	Participants will complete two online surveys that will last approximately 1h each. The survey will collect data on AUD severity, demographics, patterns of alcohol consumption, DD, and alcohol demand pre and post exposure to scarcity narrative.
Study Duration for Individual Participants	The study will have a duration of two online sessions of approximately 1h each.
Acronyms and Definitions	AUD = Alcohol Use Disorder SUD = Substance Use Disorder DD = Delay Discounting RP = Reinforcer Pathology AI = Artificial Intelligence

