3.0 Background

3.1 Summarize the relevant prior research on this topic and gaps in current knowledge within the field of study:

RP suggests that substance use disorders results from a short temporal window of reinforcer integration, as indexed by a high DD rate. Data shows that DD serves as a behavioral marker for addiction and a predictor for therapeutic outcomes. Furthermore, a short temporal window increases the valuation of brief, immediate, and intense reinforcers (e.g., drugs), and decreases the value of reinforcers that are less intense and variable over time. RP has been mechanistically tested with manipulations that both increase the temporal window (i.e., decreases DD), such as episodic future thinking, or decrease the temporal window (i.e., increases DD), such as exposure to scarcity narratives. Although exposure to scarcity narratives has been shown to increase DD, few studies have investigated its effects on alcohol valuation, as measured through demand. Thus, the goal of the present study is to investigate the effects of scarcity narratives on both DD and demand in participants with AUD.

3.2 Describe any relevant preliminary data:

Previous online and in-laboratory studies from our group and others have shown that exposure to scarcity narratives increase DD in individuals with AUD, cocaine use disorder, smokers, overweight, and obese population. However, empirical evidence on the effects of scarcity on demand and drug valuation are scarcer.

3.3 Based on the existing literature, provide the scientific or scholarly rationale for and significance of your research and how will it add to existing knowledge:

To date, only two studies investigated the effect of scarcity narrative on DD in AUD population. Furthermore, only one of them included demand measures to assess alcohol

valuation. Thus, it is unclear how exposure to a scarcity narrative impacts both DD and alcohol valuation in AUD participants. In this study, we hypothesize that exposure to active scarcity narratives will increase DD and alcohol valuation as measured through demand compared to exposure to a control narrative. Specifically, we expect that participants exposed to an active scarcity narrative will present a shorten temporal view, as measured by Delay Discounting (DD), and increase demand for alcohol compared to baseline, whereas the control group would not show any changes between baseline and post intervention measures.

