5.0 Study Design and Statistical Analysis Plan

5.1 *Describe the basic study design/approach (e.g., qualitative study using five focus groups of first year students to describe assimilation into the university community; randomized controlled trial of a behavioral change intervention to increase dietary intake of whole grains; pre- post-test evaluation of new pedagogical techniques to improve adult literacy):*

The study will use a within-between design. Adults with AUD will be randomly assigned to two groups (active or control), balanced by discounting rate and sex. All participants will provide measures for all assessments pre and post exposure to the scarcity (or control) narrative.

5.2 *Describe corresponding data analysis plan/approach (e.g., content analysis of focus group transcripts; descriptive analysis followed by linear regression modeling; nonparametric analysis of pre- and post-test measures):*

Demographic characteristics will be summarized using descriptive statistics. We will compare outcome measures using a repeated measures ANOVA with active vs. control narratives as explanatory variables. Outcomes of interest include delay discounting and alcohol demand.

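### Does enrolling on AUDIT 16 or higher, without calling that the study's definition of AUD, leave the trial population undefined?

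*Combined protocol and SAP*

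**What the plan says.** The AUD label runs through the protocol. Section 1.0 states that "Adults with Alcohol Use Disorder (AUD) will be enrolled in the study", and its secondary objective is to "Investigate the effects of scarcity narratives on delay discounting and demand in individuals with AUD". Section 3.1 says "the goal of the present study is to investigate the effects of scarcity narratives on both DD and demand in participants with AUD", and section 3.3 gives as the gap in knowledge that "it is unclear how exposure to a scarcity narrative impacts both DD and alcohol valuation in AUD participants". Sections 5.1 and 8.1 describe the people to be randomised in the same way.

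Section 12.2 sets the entry rule. Its first inclusion criterion is that participants "demonstrate high-risk or harmful drinking (AUDIT>15; i.e., 16 or higher". The second is age 21 or older. The third is a wish to stop or reduce drinking with no imminent plan to enter treatment for AUD, and this is the only place in 12.2 where AUD appears. Section 15.3 selects database members who reported alcohol use and relies on a new screener to apply the criteria.

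On measurement, section 1.0 says "The survey will collect data on AUD severity, demographics, patterns of alcohol consumption". The instruments listed under section 8.3 cover craving, withdrawal, readiness to change and other constructs, but none is identified as measuring AUD severity. On analysis, section 5.2 says "Demographic characteristics will be summarized using descriptive statistics" and names delay discounting and alcohol demand as the outcomes of interest.

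**The concern.** The population in the objectives and the population in the entry criteria carry different names. The objectives speak of a disorder. The criteria speak of a drinking level, scored on a screening questionnaire and labelled as high-risk or harmful drinking. Nothing in the text joins the two, no diagnostic check is required, the severity measure is unnamed, and the one planned descriptive summary mentions neither AUDIT nor severity.

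What would be at stake is whom the result describes. The secondary objective and the rationale in 3.3 are explicitly about people with AUD. If a material share of participants did not have AUD, conclusions worded that way would claim more than the sample supports, and a reader working from the planned summaries alone could not tell.

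**Working it through.** **1. Do the label and the criteria contradict each other?** Someone with AUDIT 16 or higher who wants to cut down can have AUD, and nothing in 12.2 excludes AUD. The third criterion, by mentioning AUD treatment, assumes that such treatment is relevant to these participants. Read with section 1.0, 12.2 serves as the working definition of the sample. What is missing is a sentence saying so. The documents give no share of participants with AUD and no data on AUDIT 16 as a proxy, so inadequacy cannot be shown from them.

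**2. Does the label enter the sample size?** Inputs from section 14.1: f = 0.25, type 1 error 0.01, pre-post correlation 0.25, 112 completers (56 per group), 70% retention. There are two measurement times.

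- Non-centrality for the Group x Time interaction: f² x N x m / (1 - rho) = 0.0625 x 112 x 2 / 0.75 = 18.67.
- With F on 1 and 110 degrees of freedom at 0.01, power is 0.953. The smallest even N reaching 95% is 112, which matches the plan.
- Enrolment: 112 / 0.70 = 160, which also matches.

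No input is an AUD definition. The only indirect route is the effect size, which 14.1 bases on preliminary data. The documents give nothing from which to say how it would differ under another definition.

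**3. Does the label enter the randomised comparison?** Eligibility is settled by a pre-screening survey (12.1), and randomisation follows the first session (8.1). The same rule therefore governs both groups before assignment. However AUD is defined, the interaction remains a valid randomised contrast within the people enrolled. The hypothesis in 2.2 is worded for participants, and the primary objective in 1.0 concerns reinforcer pathology and the temporal window, not diagnostic status.

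**4. How strong is the evidence that severity is unmeasured or will go unreported?** Weak. The list in 8.3 is not exhaustive: it omits AUDIT, which 12.2 requires, as well as the demographics and drinking patterns that 1.0 says are collected. The template text in 8.3 and 12.1 sends data collection forms and screening surveys to a separate system, and those are not part of this document. Section 5.2 says that demographics will be summarised, but it does not say that nothing else will be.

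**5. What would new text add?** If 12.2 were declared the definition, the share meeting it would be 100% by construction, so reporting it would tell the reader nothing. If some other definition were meant, the plan gives no cut-off from which to compute a share. A baseline AUDIT row would be useful, but the score has to be obtained to screen each participant, and an analyst would normally tabulate it.

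**The case for a change.** The best case for a change is that it is cheap and that the AUD claim is the study's stated contribution. One sentence in 12.2, a named severity measure and two baseline rows would let a reader match the conclusion to the sample, with no new test and no change to enrolment. The plan's own wording for its threshold is high-risk or harmful drinking, so equating it with AUD is left to the reader.

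That stands as an editorial suggestion. It does not show a defect in the design or analysis, since the cost of leaving the text alone is limited to wording that the published criteria already let a reader check.

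Two related points carry no weight. Section 26.1 mentions recruiting people in recovery from AUD, but it describes the team's past record in support of feasibility, not this sample. The change log records that the AUDIT requirement was lowered on 02/26/2024. That is not an error, and neither the earlier value nor enrolment by that date is given.

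**Conclusion.** The text does lack an explicit link between its entry criteria and the AUD label, and it does not name its severity measure. The consequence is confined to how the sample is described. The randomised comparison, the 112 completers, the 160 to be consented and the reproduced power of 0.953 do not depend on the label, and the documents give no basis for putting a number on any mislabelling.

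This is a gap that analysts fill sensibly: report the eligibility criteria as written, tabulate baseline AUDIT with whatever severity measure was collected, and word conclusions to match. The verdict rests on two assumptions: that the screening AUDIT scores are kept, and that the report states the 12.2 criteria. On that footing no change to the plan is needed.

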13.0 Vulnerable Populations

13.1 If the research involves individuals who are vulnerable to coercion or undue influence, please describe additional safeguards you will include to protect their rights and welfare. Consider the applicable items listed below:

- *If the research involves Virginia Tech students, indicate whether these are students of any of the investigators. If so, describe whether*

the activities will take place during class time as part of the curriculum and the steps you will take to reduce the possibility that students feel obliged to participate in order to improve their course grade. The HRPP can provide further guidance as needed. Describe whether you will request access to student records (e.g., SAT, GPA, GRE scores).

- *If the research involves employees of Virginia Tech or the research sponsor, describe steps you will take to ensure that the employees are freely participating and describe how their data will be protected from inspection by their supervisors.*
- *If the research involves Virginia Tech NCAA athletes, you must obtain approval from the athletic department.*
- *For research involving Montgomery County Public Schools, you must obtain county approval (after obtaining contingent Virginia Tech approval). Other locales have different requirements; please check on these and describe here. Approval is typically granted by the superintendent, principal, and classroom teacher (in that order). Approval by an individual teacher is insufficient. School approval, in the form of a letter or a memorandum should be uploaded as a supporting document.*
- *If the research involves pregnant women, review “CHECKLIST: Pregnant Women (HRP-412)” to ensure that you have provided sufficient information in this protocol.*
- *If the research involves prisoners, review “CHECKLIST: Prisoners (HRP-415)” to ensure that you have provided sufficient information in this protocol.*
- *If the research involves persons who have not attained the legal age for consent to treatments or procedures involved in the research (minors), review the “CHECKLIST: Minors (HRP-416)” to ensure that you have provided sufficient information in this protocol.*
- *If the research involves cognitively impaired adults, review “CHECKLIST: Cognitively Impaired Adults (HRP-417)” to ensure that you have provided sufficient information in this protocol.*

This research study will not include any vulnerable populations.

